6.2. Anticipated Length of Study

Recruitment for the study is expected to take approximately 2-3 months. Each participant is expected to complete the study in approximately 2 months from time of enrollment with all participants complete within a total of 6 months. Lab assays will begin once the first participant completes all visits and will continue until the last participant. Data analysis is expected to take approximately 3 months and preparation of the final report 2 additional months.

6.3. Number of Subjects

Approximately 20 women may be consented and undergo assessment procedures in order to have approximately 14 women who meet eligibility criteria complete the study. All 14 women will be randomly assigned to undergo either a low adherence dosing or high adherence dosing. All randomized participants will be included in the analysis.

6.4. Treatment Assignment

Women will be randomized to one of two in two dosing regimens of oral tablets: TDF/FTC (300/200 mg), 7 pills per week and TDF/FTC (300/200mg), 3 pills per week.

6.5. Criteria for Study Termination

Recruitment for the study or a treatment arm may be stopped if, in the opinion of the grant principle investigator:

- The site has failed to enroll participants at an acceptable rate
- The protocol requirements have not been adhered to, and/or
- Administrative reasons

7. SELECTION AND WITHDRAWAL OF PARTICIPANTS

The volunteers for this study will be recruited primarily through word of mouth and by using existing databases of previous study participants (as protected health information permits.)

Only women will be recruited since the endpoints require vaginal sampling. The NIH has mandated that children, defined as younger than 18 years old, be included in research trials when appropriate. This study meets “Justifications for Exclusion” criteria for younger children as set forth by the NIH (specifically, “insufficient data are available in adults to judge potential risk in children” and “children should not be the initial group to be involved in research studies”). As such, this study does not plan to enroll children. Efforts will be made by the sites to recruit participants so that the racial and ethnic characteristics of the subject population will reflect the demographics of the study sites. No selection criteria shall be based on race or ethnicity.

7.1. Inclusion Criteria

Volunteers must meet all of the following criteria prior to baseline sampling at visit 2:

1. Age 18 to 50 years, inclusive
2. General good health (by volunteer history and per investigator judgment) without any clinically significant systemic disease (including, but not limited to significant liver disease/hepatitis, gastrointestinal disease, kidney disease, thyroid disease, osteoporosis or bone disease, and diabetes) and with an intact gastrointestinal tract, uterus and cervix.
3. Estimated calculated creatinine clearance (eCcr) of at least 80 mL/min
4. Body Mass Index (BMI) of ≥ 18 and $< 35 \text{ kg/m}^2$; and a total body weight $> 45 \text{ kg}$ (99.2 lbs)
5. Willing to give voluntary consent and sign an informed consent form
6. Willing and able to comply with protocol requirements, including swallowing tablets
7. Must be protected from pregnancy by:
 - Condoms
 - Hormonal contraceptives
 - Copper or Levonorgestrel IUD
 - Sterilization of either partner
 - Heterosexual abstinence
 - Same sex relationship
8. If in a relationship, must be in a mutually monogamous relationship with a partner who is not known to be HIV positive and has no known risk of STIs

7.2. Exclusion Criteria

Volunteers must not meet any of the following criteria prior to baseline sampling:

1. Currently pregnant
2. Currently breastfeeding or planning to breastfeed during the course of the study
3. In the last three months, diagnosed with or treated for any STI

4. Positive test for HIV, or Hepatitis B surface antigen (HBsAg)
5. Systemic use in the last two weeks or anticipated use during the study of any of the following: antiretrovirals (e.g. Viread®, Atripla®, Emtriva®, or Complera®), or drugs that may interact with TFV (e.g., protease inhibitors, anticonvulsants, antimycobacterials, St. John's Wort).
6. Participation in any other investigational trial with use of a drug/device within the last 30 days or planned participation in any other investigational trial with use of a drug/device during the study
7. Grade 2 or higher laboratory abnormality, per the 2014 update of the Division of AIDS, National Institute of Allergy and Infectious Disease (DAIDS) Table for Grading the Severity of Adverse Events, or clinically significant laboratory abnormality as determined by the clinician
8. Abnormal finding on laboratory or physical examination or a social or medical condition in the volunteer which, in the opinion of the investigator, would make participation in the study unsafe or would complicate interpretation of data

7.3. Participant Withdrawal

7.3.1. Withdrawal Criteria

Participants who sign the informed consent and agree to participate in the study, but do not meet eligibility criteria will not undergo baseline sampling and will not continue in the study. Once a participant undergoes baseline genital/rectal sampling, she may be withdrawn from the study for the following reasons:

- Failure to follow protocol requirements that is judged severe enough by the investigator to significantly affect study outcomes
- Pregnancy or desire to become pregnant
- Medical reasons, including diagnosis of an STI
- Personal reasons (participant request)
- Discontinuation of treatment adherence arm, or of entire study (Section 6.5)

7.3.2. Target Enrollment

Participants who initiate product use but discontinue the study prior to completion may not re-enroll. Participants will be screened and enrolled so that approximately 14 women (7 per adherence cohort) complete all study visits.

7.3.3. Follow-up

If a participant chooses to discontinue the study after baseline sampling, the site may ask the participant to return for the next visit's study procedures, if she is willing and if relevant. She will be asked about medications taken and adverse events (AEs) since the last visit. She will be exited from the study during her last contact with the site.

8. STUDY PROCEDURES

Prospective participants may be pre-screened by telephone or in person: the study will be explained, the inclusion/exclusion criteria reviewed, volunteers' questions answered, and Visit 1 scheduled.

8.1. Visit 1: Screening/Enrolment

The following will take place to confirm the volunteer is eligible to continue in the study. Note that if the participant is not able to complete any of the study procedures at this visit, she may return for an unscheduled visit prior to Visit 2.

- The study and informed consent form will be reviewed and all volunteer questions will be answered. If the volunteer is eligible and wishes to participate in the study, she will be asked to sign an informed consent form. The Principal Investigator (PI) or designee will sign the form and offer a copy to the participant. Permission may be requested as part of the informed consent process for storage of the biologic samples obtained during the study for possible future testing, as allowed by the site.
- The informed consent process will include an explanation of adherence support (e.g., text message reminders) and a request for permission to contact the participant for this purpose.
- The participant will be interviewed to obtain medical history and demographic information.
- Height, weight, and blood pressure will be measured and recorded.
- A urine specimen will be obtained for a urine pregnancy test. If the pregnancy test is positive, the participant will be referred as necessary and will not continue in the study.
- If the participant's history is significant for a medical condition, a directed physical exam and or pelvic exam will be performed as necessary.
- Blood samples (approximately 4 teaspoons) will be collected for HIV and HBsAg testing as well as serum creatinine to calculate a creatinine clearance. Participants who test HIV or HBsAg positive at screening are not eligible to continue in the study. They will be counseled and given referrals for medical and social services.

Eligible participants will be scheduled for the next visit and directed to refrain from vaginal intercourse for 48 hours prior to visit 2.

8.2. Visit 2: Baseline Pre-Dose Sample Collection

This visit will be scheduled for the early follicular phase of the menstrual cycle (for cycling women).

- An interval history will be collected.
- Eligibility criteria will be reviewed. If any lab tests reveal that the participant is not eligible, the visit should not proceed and the participant will not continue in the study.
- If indicated by signs or symptoms or history, a directed physical exam and/or urine pregnancy test will be performed. If pregnancy is diagnosed, the participant will be referred as necessary and will be discontinued.

- A vaginal swab for prostate specific antigen (PSA) will be obtained, if the PSA test indicates semen exposure, the visit will be re-scheduled.
- A urine sample will be obtained.
- Vaginal swabs will be obtained
- A blood sample (approximately 2 teaspoons) will be obtained.
- The participant will be randomized to the HA versus LA regimen and will take her first doses of TDF/FTC in the clinic under direct observation and the time of product ingestion will be recorded in the source document. The pill will be ingested after urine, vaginal and blood samples are obtained.
- The participant will confirm her contact information for the medication text reminder.
- Participants will be instructed to refrain from vaginal intercourse for 48 hours prior to visits 3 – 5.

8.3. Visits 3 – 5: 24 hours , 7 days, and 14 days after first dose

Visits 3, 4, and 5 will be scheduled for 24 hours, 7 days, and 14 days after initial dosing at Visit 2, respectively. The time of the visit will assure that it has been at least 24 hours since the participant's last dose of TDF/FTC. At each visit, the following procedures will be performed:

- The study staff will ask the participant if she followed the instructions from the previous visit, and ask about adverse events and concomitant medications.
- If indicated, a directed physical exam, pelvic exam and/or pregnancy test will be performed. If pregnancy is diagnosed, the participant will be referred as necessary and will be discontinued.
- Visits 4 and 5: Study staff will count the number of pills remaining and query the participant on compliance with her assigned dosing regimen.
- A vaginal swab for PSA will be obtained, if the PSA test indicates semen exposure, the participant will be reminded of the restrictions on vaginal intercourse, but the visit will proceed.
- A urine sample will be obtained.
- Vaginal swabs will be obtained
- A blood sample (approximately 2 teaspoons) will be obtained.
- Visits 3 and 4: The participant will take her dose of medication in the clinic, under direct observation, if applicable to her dosing regimen, after urine, vaginal and blood samples are obtained.
- Visits 3 and 4: Study staff will dispense the appropriate number of TDF/FTC pills in a pill carrying case, so that the participant has enough pills to take her to before her next scheduled visit.

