12.4. Pregnancy Screen

A pregnancy test is required at Visit 1. Note that participants must be protected from pregnancy as described in Section 7.1 in order to be eligible for study participation. A pregnancy test will be done at subsequent visits, if indicated by participant signs and symptoms.

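### Pregnancy is an exclusion that applies just before baseline sampling at Visit 2, but the only required test is at Visit 1, with no limit on its age and two different triggers for repeating it

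*Combined protocol and SAP*

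**What the plan says.** Section 7.2 introduces its list with "Volunteers must not meet any of the following criteria prior to baseline sampling", and the first item is "Currently pregnant". Section 7.1 places the inclusion criteria at the same moment and names Visit 2.

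On testing, section 12.4 states "A pregnancy test is required at Visit 1" and then "A pregnancy test will be done at subsequent visits, if indicated by participant signs and symptoms". Section 8.2, which governs Visit 2, states "If indicated by signs or symptoms or history, a directed physical exam and/or urine pregnancy test will be performed". In Table 4 the urine pregnancy test has a plain tick at Visit 1 and bracketed ticks afterwards, and the key explains brackets as conditional.

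On timing, section 8.1 ends with "Eligible participants will be scheduled for the next visit and directed to refrain from vaginal intercourse for 48 hours prior to visit 2". It gives no latest date for that visit. Section 15.2 sets windows for Visits 3, 4 and 5 only, each counted from the first dose. Section 8.2 places Visit 2 in the early follicular phase, for cycling women.

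At Visit 2 a vaginal swab is tested for prostate specific antigen (PSA), and "if the PSA test indicates semen exposure, the visit will be re-scheduled". Urine, vaginal and blood samples are then taken, the woman is randomized, and she takes the first tablet under observation.

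**The concern.** The protocol fixes the time at which exclusion 1 must be clear, but it does not require an objective check at that time. The one mandatory result comes from an earlier visit, and nothing limits how much earlier. The conditional test at Visit 2 depends on what the woman reports or shows, and the two sections that define its trigger do not match.

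What is at stake is participant safety. The protocol treats pregnancy as an exclusion, as a reason to discontinue, and, once there has been exposure to product, as something to follow to its outcome (section 13.3). An exposure that a test on urine already in hand could have prevented would be hard to defend.

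**Working it through.** The plan states no figure to reproduce on this point, and the conclusion needs no sample size, power or error rate. The check sets the sections side by side.

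1. **When the criterion applies.** Before baseline sampling at Visit 2 (7.1, 7.2).
2. **When a test is required.** Visit 1 only (8.1, 12.4; plain tick in Table 4).
3. **How far apart steps 1 and 2 may be.** Section 8.1 says only that the next visit will be scheduled. Section 15.2 starts its windows at the first dose, so it does not reach back to Visit 1. Section 6.2 offers "Each participant is expected to complete the study in approximately 2 months from time of enrollment", which is an expectation for the whole of a woman's participation and not a limit on this interval. No maximum is stated.
4. **What prompts a repeat test.** Section 8.2 accepts signs, symptoms or history. Section 12.4, which covers all visits after Visit 1, accepts signs and symptoms only. Section 8.3 says only that a test is done when indicated. A woman with a suggestive history and no symptoms qualifies for a test at Visit 2 under 8.2 and does not under 12.4.
5. **What follows at Visit 2.** Randomization and the first tablet, at the same visit (8.2).

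From 1 to 5: if every section is followed exactly, a woman with no signs, symptoms or suggestive history reaches the first tablet with her Visit 1 result as the only test, whatever its age.

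**The PSA branch.** The stated consequence of a semen-positive swab is that Visit 2 is rescheduled. Under the 8.2 trigger, staff could treat the result as history and test. Under the 12.4 trigger, the result would not itself prompt a test, because it is neither a sign nor a symptom of pregnancy. Which applies depends on which section the site follows.

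**Cost of closing the gap.** Urine is already collected at Visit 2 before the tablet. Section 6.3 expects about 14 women to complete and about 20 to be consented, so one test per woman is about 14 to 20 strips.

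**The case against.** The strongest reply is that Visit 2 is not unguarded. It includes an interval history, a review of the eligibility criteria and a test when indicated, and a rescheduled Visit 2 would repeat all three. Early-follicular timing makes an unnoticed pregnancy less likely, and the synopsis describes women with regular cycles. The women most likely to lack cycle timing, users of hormonal methods or the levonorgestrel IUD, are protected by those methods. Exclusion 1 does not ask for a same-day test, so the sections do not strictly contradict one another on that.

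Much of this stands, and it makes the residual risk small. It does not close the gap. The history and the review rely on report and require no new result. The follicular timing is limited to cycling women, and section 7.1 does not carry over the regular-cycle description from the synopsis. The mismatch between 8.2 and 12.4 remains.

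A reader might infer more than the documents support:

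- **That a positive PSA proves inclusion 7 was not met.** It shows semen exposure. For a woman using an IUD, a hormonal method or sterilization it says nothing about inclusion 7. For a condom user it does not separate non-use from failure. It is a direct contradiction only for heterosexual abstinence.
- **That the Visit 1 result will be a month or more old.** Taking about 60 days from 6.2, less 14 days of visits and 7 to 14 days to the follow-up contact, leaves 60 − 14 − 14 = 32 to 60 − 14 − 7 = 39 days. That assigns all the slack in an approximate expectation to one interval, which the protocol does not do. Adding a further cycle after a reschedule is an assumption, since 8.2 gives no length of delay.
- **That the analysis would suffer.** Section 7.3.2 enrols until about 14 women, 7 per cohort, complete all visits, so a discontinuation can be made up.
- **That the HIV, HBsAg and creatinine results have the same problem.** No validity period is given for them, but that is missing detail with no demonstrated failure behind it.

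**Conclusion.** The point holds as a gap in verifying eligibility. The protocol says when exclusion 1 applies, requires a test only at an earlier visit, puts no limit on the interval, and gives two different triggers for repeating the test. Dosing on a Visit 1 result of any age is therefore consistent with the plan as written.

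Its size cannot be expressed as a probability, because the documents give neither a planned Visit 1 to Visit 2 interval nor a pregnancy rate. The existing safeguards make the event unlikely in a study of about 14 women. No endpoint, estimate or sample-size statement changes. The case for acting rests on the seriousness of an avoidable exposure set against a very low cost.

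The conclusion assumes that no separate site procedure already requires a test at Visit 2. The protocol does not mention one.

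**What to change.** Reconcile 7.2, 8.2, 12.4 and Table 4 so that exclusion 1 is verified when 7.2 says it applies:

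- In 8.2, 12.4 and the Visit 2 column of Table 4, make the urine pregnancy test a required eligibility check, and say that this includes a rescheduled Visit 2.
- State that it is run on the urine already collected at that visit and read before randomization and the first tablet. In 8.2 the eligibility review is listed before the urine sample, so say that the review is complete only once the result is known.
- Use one trigger wording in 8.2, 8.3 and 12.4 for the conditional tests at later visits.

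What happens after a positive result is already set out in 8.2 and need not change. The downside is about 14 to 20 test strips and a short wait for the result at Visit 2. No dose, sampling time or analysis is altered.

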8.4. Final Follow Up Contact

The site will contact the participant approximately 1 - 2 weeks after the last visit. The participant will be asked about any AEs and concomitant medications since her last visit. The participant will be exited from the study unless symptoms require further follow up or she is appropriately referred.

8.5. Unscheduled Visits

The participant will be instructed to contact the site if she experiences moderate to severe symptoms (e.g. gastrointestinal symptoms).

Unscheduled visits or procedures (e.g. urinalysis, vital sign measurements) may be performed at the participant's request or as deemed necessary by the investigator at any time during the study. The participant will be asked to come in for an evaluation, as indicated. Unscheduled visits that require examination or interview due to symptoms will be in the study database.

When an unscheduled visit occurs in response to an AE experienced by a study participant, study staff will assess the reported event clinically and provide or refer the participant to appropriate medical care, as necessary. All AEs will be evaluated and follow-up of any observed abnormalities will proceed according to the study manual.

8.6. Early Discontinuation

If the participant discontinues from the study prior to the final visit, the site may ask the participant to return for study procedures and/or sample collection, if she is willing and if relevant. At a minimum, the site may ask participants to return for safety assessments. She will be asked about medications taken and adverse events including symptoms since the last visit. She will be exited from the study during her last contact with the site.

9. TREATMENT OF PARTICIPANTS

9.1. Study Products

Table 5 provides a summary of the treatment to be administered, including the doses and route of administration.

Table 5: Emtricitabine/tenofovir disoproxil fumarate (FTC/TDF 200/300 mg)

Product Name	emtricitabine/tenofovir disoproxil fumarate (FTC/TDF) (Truvada®)
Unit Dose	200 mg FTC / 300 mg TDF
Dosage Form	Tablet
Route of Administration	Oral
Physical Description	The tablets are blue, capsule-shaped, film-coated, and debossed with “GILEAD” on one side and with “701” on the other side
Manufacturer	Gilead Sciences, Inc. (Foster City, CA USA)

9.2. Concomitant Medications

All concomitant medications will be recorded on source documents and the study database for participants who have undergone baseline genital/rectal sampling.

Antriretrovirals (e.g., Viread®, Atripla®, Emtriva®, or Complera®), or drugs that may interact with TFV (e.g., protease inhibitors, anticonvulsants, antimycobacterials, St. John’s Wort) should not be used during the study (see Section 7.2).

9.3. Treatment Compliance

Treatment compliance will be evaluated by directly observed therapy (in-clinic dosing) at visits 2, 3 and 4, as appropriate to the participant’s dosing regimen, participant report and returned tablet count.

9.4. Randomization and Blinding

This is a prospective, randomized trial. Participants and clinical study staff will not be blinded to the adherence dosing regimen. The laboratories and statistical/data analysts will be blinded to study treatment. Participants will be randomized 1:1 to the HA versus LA regimen, by simple randomization.

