5. TRIAL PURPOSE, OBJECTIVES AND ENDPOINTS

5.1. Purpose

The purpose of this study is to assess the sensitivity and specificity of the TFV aptamer-based biosensor measuring TFV levels in plasma, urine, and vaginal fluid and its ability to monitor adherence to antiretroviral therapy. The concentrations measured with aptamer-based biosensor will be compared to concentrations measured via LC-MS/MS, which is currently the gold standard for pharmacokinetic analysis of TFV.

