5.2.1. Primary Objectives

- Compare plasma TFV concentrations measured by the aptasensor with those values quantitated by LC-MS/MS to determine agreement between the two methodologies, sensitivity, specificity, NPV, and PPV
- Determine if the TFV aptasensor can detect differences in the plasma TFV concentrations between high and low adherence dosing regimens and compare the mean difference to the difference calculated from values generated by LC-MS/MS

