14.4. Statistical Analysis

Sample size is based on feasibility rather than statistical considerations; thus, analysis will be primarily descriptive. Participant flowchart (e.g. number screened, number with sampling) will be provided. All populations will be defined based on the adherence regimen.

Evaluation of Study Objectives: Study objectives will be evaluated by clinical review of descriptive summaries and graphical displays.

Primary analysis of this study will evaluate the performance of the TFV aptasensor by comparing its measurements of the concentrations of TFV in clinical samples from all women with those values obtained from LC-MS/MS. Correlation and agreement between the TFV levels measured by the aptasensor and LC-MS/MS will be analyzed using scatterplot and linear regression. Continuous variables will be compared between values measured with the aptasensor versus LC-MS/MS using paired comparisons. From this comparison, sensitivity, specificity, NPV, and PPV of the aptasensor will also be determined. Confidence intervals will be calculated to assess precision and margin of error of those

measures. Using the 14 baseline pre-dose samples, each woman will be her own control, and these pre-dose samples will be used for the assessment of specificity and NPV.

The secondary analysis of this study will evaluate whether the aptasensor can detect differences in TFV levels between the two independent cohorts of women taking TDF/FTC at different dosing regimens representing high (7 pills/week) and low adherence (3 pills/week). We will compare the two independent cohorts using an independent samples t test for normally distributed data or a Wilcoxon-Mann-Whitney test for non-parametric data. TFV concentrations from the LA and HA cohorts will be characterized using descriptive statistics (mean, median, interquartile range, minimum and maximum). The values will be compared between the high adherence and low adherence groups as well as comparing the mean difference between groups generated by the aptasensor to that difference generated by LC-MS/ MS. Distributions will be checked to determine normality so as to determine the appropriate statistical test.

Descriptive Statistics: Categorical variables will be summarized by frequencies and percentages. Continuous variables will be summarized by means, standard deviations, medians, quartiles, minima and maxima.

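### Laboratory blinding is stated for regimen only; the documents state no masking of visit (pre-dose status) or of the other assay's result, which matter most for the agreement and specificity analysis

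*Combined protocol and SAP*

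**What the plan says.** Section 9.4 of the combined protocol and SAP is the only text on blinding. It first leaves the clinic open: "Participants and clinical study staff will not be blinded to the adherence dosing regimen". It then adds: "The laboratories and statistical/data analysts will be blinded to study treatment". The sentence after that gives the 1:1 allocation to HA or LA.

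Section 5.2.1 lists two primary objectives. The first is a method comparison: "Compare plasma TFV concentrations measured by the aptasensor with those values quantitated by LC-MS/MS to determine agreement between the two methodologies", together with sensitivity, specificity, NPV and PPV. The second asks whether the sensor detects a difference in plasma TFV between HA and LA, and how that difference compares with the one from LC-MS/MS. Section 5.1 describes LC-MS/MS as the method "which is currently the gold standard for pharmacokinetic analysis of TFV".

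Section 14.4 makes the method comparison the primary analysis, "comparing its measurements of the concentrations of TFV in clinical samples from all women with those values obtained from LC-MS/MS". On the negatives, 14 in number with one from each participant, it says that "these pre-dose samples will be used for the assessment of specificity and NPV".

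On timing, section 6.2 says: "Lab assays will begin once the first participant completes all visits and will continue until the last participant". Section 15.2 has the site record the date and time of every collection.

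**The concern.** Blinding should hide whatever would tell the reader of an assay what the answer ought to be. For an HA versus LA contrast, that is the regimen. For a paired comparison of two assays on the same samples, pooled over regimen, the regimen says little about any single pair. Two other facts say much more.

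The first is the visit. Recent antiretroviral use is an exclusion (section 7.2), and the first tablet is swallowed only after the Visit 2 samples are taken (section 8.2). A tube known to be from Visit 2 is therefore known to be an expected negative. The second is the LC-MS/MS value, because the sensor is judged against it.

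Both assays are quantitative, so bias would have to enter where there is discretion: repeating or rejecting a run, recalibrating, handling values near the detection limit, or choosing the positivity cut-off. The documents set no cut-off, no repeat rule and no rejection rule. If those choices were made by someone who knew the expected answer, they would tend to flatter the sensor. The Synopsis says the statistics are to guide further development of the aptasensor, and that use depends on an honest accuracy estimate. Readings made unmasked cannot be masked afterwards.

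**Working it through.** The plan contains no figure to reproduce. Section 14.1 sets the sample size by feasibility. The check is therefore a comparison of texts, followed by a calculation of how sensitive specificity is to a single call.

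**Step 1. What the stated rule covers.**

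| Information | Stated as masked from laboratories and analysts? | Objective it bears on most |
|---|---|---|
| HA or LA regimen | Yes (9.4) | Second primary objective (HA versus LA) |
| Visit, hence pre-dose status | Not stated | First primary objective: specificity and NPV |
| Result of the other assay | Not stated | First primary objective: agreement and all accuracy measures |

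The term study treatment in 9.4 stands between a sentence on dosing regimen and a sentence on HA/LA allocation, so regimen is its natural meaning. It could be stretched to cover dosed versus not-yet-dosed status, but the text does not say so. No reading extends it to the other assay's result. Nothing else in the documents mentions sample coding, run order, access to results across assays, or a data lock before linkage.

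**Step 2. What one call is worth.** Input: 14 pre-dose samples as negatives (14.4).

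- One call = 1/14 = 7.1 percentage points of specificity.
- 14/14 = 100%. Exact (Clopper-Pearson) lower 95% limit = 0.025^(1/14) = 76.8%.
- 13/14 = 92.9%. Lower limit: the p at which P(X ≥ 13 | n = 14, p) = 0.025, which is 66.1%. Upper limit: 0.975^(1/14) = 99.8%.
- 12/14 = 85.7%, exact 95% CI 57.2% to 98.2%.

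**Step 3. Would a positive pre-dose reading arise at all?** The documents give no expected specificity, so the values below are assumptions. The chance of at least one false positive among 14 is 1 − s^14:

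| Assumed true specificity s | s^14 | Chance of at least one false positive |
|---|---|---|
| 95% | 0.488 | 51% |
| 90% | 0.229 | 77% |
| 80% | 0.044 | 96% |

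So a reading that might invite a second look is plausible across this range. Whether anyone would repeat or re-call it, and whether they would know it was pre-dose, is not in the documents.

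**Step 4. Sample count for the fix.** 14 women × 4 sampling visits (Visits 2 to 5) = 56 samples per fluid. Where each sample is split between the two methods, 56 × 2 = 112 aliquots.

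**The case against.** The best answer is that silence is not exposure. Section 9.4 does blind the laboratories. Nothing says that tubes arrive with visit labels or that one laboratory receives the other's values, and section 15.2 has collection times recorded at the site without saying that laboratories see them. Sample coding often sits in a laboratory manual, which cannot be checked here. That stands: the supported statement is that masking of visit and of the other result is not stated. A reader might infer that operators will know both, and the documents do not show that.

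A reader might also infer from section 6.2 that LC-MS/MS results will be on hand while sensor readings are still being finalised. That section gives only when assays start and end. It does not say which method runs first, whether either is batched, or when results are released. Overlap is a possibility, not a described workflow.

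It would also be wrong to conclude that the existing blinding does no work. It directly serves the second primary objective and should stay.

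Finally, the move from 13/14 to 14/14 is what one changed call does for any reason. It shows how coarse a sample of 14 is and does not measure bias, and the two intervals overlap heavily.

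The descriptive, pilot nature of the study does not dispose of the point. The caution in section 14.4 concerns Type I error and multiplicity, whereas readings influenced by knowledge of the expected answer would bias the estimates themselves.

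**Conclusion.** The point holds as a gap in the stated safeguard. The documents mask regimen, which suits the second primary objective, and state no masking of the two facts that bear most on the first. The bias is conditional on three things that the documents leave open: that operators have the information, that they have discretion over readings or cut-off, and that they use it. Its size cannot be estimated from the documents. What can be said is that each changed call among the 14 negatives moves specificity by 7.1 points, and that at an assumed true specificity of 80% to 95% the chance of at least one false positive among them is 96% to 51%. The 7.1 points should not be read as an expected bias.

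The change is worth making before assays begin, because it is cheap and closes a route to bias in the primary analysis. If a laboratory manual already provides for it, a reference to that manual in 9.4 would settle the point.

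**What to change.** Keep the regimen blinding and extend section 9.4 to state that:

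1. aliquots carry accession codes that reveal neither visit nor participant;
2. run order is randomised within each assay batch. Full randomisation across the study would have to wait for the last participant and would conflict with the rolling start in section 6.2, whereas randomising within batch does not;
3. operators of each assay are masked to visit and to the other assay's results;
4. all sensor readings including repeats, the rule for which repeat is analysed, and the positivity cut-off are locked before LC-MS/MS values and visit codes are linked. Locking the readings alone would still allow a cut-off to be chosen after linkage that gives 14/14.

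Cost: coding about 56 samples per fluid, or about 112 aliquots where a sample is split between the two methods, and having existing staff who are not involved in the assays hold the linking list. Randomising within batch protects less than full randomisation would, since a small batch leaves fewer possible orders. No extra participants, samples or assays are needed.
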